1. PURPOSE

The purpose of this post-marketing clinical use surveillance (hereinafter referred to as “Surveillance”) is to observe the frequency, type and degree of adverse device effects and adverse events in order to assure the safety of the new medical device, and to collect safety and efficacy information for evaluating the results of the clinical use. The Surveillance will be conducted per the standards required by the Minister of Health, Labour and Welfare (MHLW) and in the standards for post-marketing surveillances and studies [except for those defined in the Ministerial Ordinance on Good Clinical Practice for Medical Devices (MHLW Ordinance No. 36, 2005)] based on Paragraph 4, Article 23-2-9 (including application *mutatis mutandis* per Article 23-2-19 of Revised PAL) of the Law on Securing Quality, Efficacy and Safety of Pharmaceuticals and Medical Devices, etc. (Law No. 145, 1960, hereinafter referred to as “Revised PAL”) by the Marketing Authorization Holder or accredited foreign manufacturer of a medical device defined in Paragraph 1, Article 23-2-5 of Revised PAL.

2. SURVEILLANCE METHOD

2.1 Patients

Based on the Ministerial Ordinance on Good Post-marketing Study Practice for Medical Device, the Surveillance will **consecutively register** patients with moderate to severe and severe mitral regurgitation (3+ and 4+ MR) in whom a MitraClip implant was attempted (Marketing Approval No. 22900BZX00358000, October 31, 2017, hereinafter referred to as “MitraClip”). Patients registered in the AVJ-514 clinical trial who received additional MitraClip procedures will be excluded from the Surveillance.

2.2 Registration Method

- Patient registration will occur consecutively when treatment with MitraClip is attempted. Patients registered in the AVJ-514 clinical trial who received additional MitraClip procedures will be excluded from the Surveillance.
 - Patients will be considered registered upon femoral vein puncture for transseptal access in preparation for MitraClip System insertion.
 - If an attempt of MitraClip implantation failed with subsequent treatment done with other device(s) or surgical repair, only the information on the attempted MitraClip implant will be recorded. For this patient, follow-up is not required unless any adverse event occurred in relation to the attempted MitraClip implantation.
- It is not recommended that patients registered in the Surveillance participate in any other therapeutic clinical study. Registered patients can participate in non-therapeutic clinical studies, such as non-invasive cardiac imaging study.

2.3 Planned Sample Size

The target sample size of this surveillance is up to patients at up to Japanese sites.

3. SURVEILLANCE PERIOD

Information will be collected for up to 3 years post procedure. The target registration period will be from the date that patient registration is allowed upon execution of study agreement with each site to the last patient registered into the PMS. Shown below are specific details associated with the surveillance period.

- Approximate preparation period: 6 months
- Registration period: the estimate of the registration period for the PMS is about 2 years
- Follow-up period: 3 years
- Final re-examination report: 6 months
- Total PMS period: Approximately 6 years

Primary analysis data will be collected until all patients complete 30 days follow-up. Annual progress reports (up to 3 years) will be submitted to the regulatory authority at each time point accordingly.

Data will be collected at the following time points:

- Baseline (pre-procedure)
- Procedure
- Discharge
- 30 days (30 days+14 days) (by visit)
- 1 year (365 days±28 days) (by visit)
- 2 years (730 days±28 days) (by visit)
- 3 years (1095 days±28 days) (by visit)

4. TREATMENT OF PATIENTS

The MitraClip NT will be implanted per the current approved instructions for use (IFU). Physicians should refer to the warnings, contraindications, and precautions in the most current version of product IFU for optimal treatment of each patient.

5. INFORMATION TO BE COLLECTED FOR THE SURVEILLANCE

5.1 Baseline

1) **Basic Patient Information**

- Registration date
- Date of birth or age at procedure
- Gender
- Height
- Weight

2) **Cardiac Status at Registration**

- Mitral regurgitation severity and etiology, as reported by site
 - Functional mitral regurgitation (FMR)
 - Degenerative mitral regurgitation (DMR)
- Ischemic status at registration, especially previous interventions
- New York Heart Association (NYHA) functional class
- Atrial fibrillation: paroxysmal, persistent, permanent
- Previous cardiac resynchronization therapy
- Previous percutaneous coronary intervention (PCI) and coronary artery bypass grafting (CABG)
- Previous heart valve surgery or other cardiothoracic surgeries
- Left ventricular function and anatomy as reported by site
 - Left ventricular ejection fraction (LVEF)
 - Left ventricular end systolic volume (LVESV), left ventricular end diastolic volume (LVEDV), left ventricular end systolic dimension (LVESD), left ventricular end diastolic dimension (LVEDD).

3) **Risk Factors and Medical History**

- General heart disease risk factors
 - Smoking status
 - Diabetes
 - Hypertension
 - Dyslipidemia
- Renal failure
 - Currently on dialysis
- Previous cerebrovascular accident (CVA)/ transient ischemic attack (TIA)
- Previous peripheral disease and intervention
- Chronic pulmonary disease
- Previous major bleeding
- Cirrhosis
- Cancer

- Subject is deemed difficult for mitral valve surgery due to either STS surgical mortality risk for mitral valve replacement of $\geq 8\%$ OR due to the presence of one of the following risk factors:
 - Porcelain aorta or mobile ascending aortic atheroma
 - Post-radiation mediastinum
 - Previous mediastinitis
 - Functional MR with LVEF $<40\%$
 - Over 75 years old with LVEF $<40\%$
 - Re-operation with patent grafts
 - Two or more prior cardiothoracic surgeries
 - Hepatic cirrhosis
 - Other surgical risk factor(s)

4) Classes of Cardiovascular and Heart Failure Medications

- Angiotensin converting enzyme (ACE) inhibitor
- Angiotensin II receptor blocker
- Aldosterone receptor blocker
- Beta-blocker
- Diuretics
- Calcium channel blocker
- Anti-Platelets
- Anticoagulants
- Antiarrhythmics
- Cardiac glycosis (Digitalis)
- Statins
- Other vasodilators
- Other cardiac medication

5) Transthoracic and Transesophageal Echocardiography

Transthoracic echocardiography (TTE) and transesophageal echocardiography (TEE) shall be performed at baseline. TTE and TEE will be used to assess the severity of mitral regurgitation, mitral valve anatomy, and left ventricular function and dimensions.

6) Pre-procedure ECG

A 12-lead electrocardiogram will be performed at baseline or prior to the procedure.

7) Pre-procedure Laboratory Tests

Standard pre-procedure lab tests, including but not limited complete blood count (CBC), cardiac biomarkers, renal function, and liver function will be performed.

8) Pre-procedure Antiplatelet Medications

Pre-procedure anticoagulation and/or antiplatelet medications will be administered per institutional standard-of-care.

5.2 MitraClip Procedure Information

1) General Information

- MitraClip Procedure date
- Operator's name
- Procedure start time (time guiding catheter inserted)
- Procedure end time (time guiding catheter removed)
- Radiation time

2) MitraClip NT Used

- Number of clips used
- Successful implantation in intended location
- Device deficiency
- Product information (Lot/Serial #)

3) Final Outcome Result

- MR severity post MitraClip NT procedure
- Procedural complications

5.3 Post-procedure (In-hospital) Information

1) Post-procedure ECG

A 12-lead electrocardiogram will be performed post-procedure.

2) Post-procedure Anticoagulation and Antiplatelet Medications

Post-procedure anticoagulation and/or antiplatelet medications will be administered per institutional standard-of-care.

3) Hospitalization Information

- Post procedure Post-Anesthesia Care Unit (PACU)/Intensive Care Unit (ICU)/ Critical Care Unit (CCU) stay (hours)
- Total hospital stay (days)

4) In-hospital Adverse Events Reported by Site

- In-hospital death
- Cardiogenic shock
- Heart failure
- CVA
- Cardiac tamponade
- Pericardial effusion
- New requirement of dialysis
- Mitral valve re-intervention, MitraClip or surgery
- Vascular complication (requiring prolongation of existing hospitalization)
- Bleeding complication within 72 hours (requiring blood transfusion or Hb drop of > 3g/dL)
 - Access site
 - Non-access site
- Device embolization
- Other adverse events

5.4 Discharge Information

- Discharge date
- Discharge TTE findings, including MR severity and LV measurements
- Heart failure condition, including NYHA class
- Discharge medications
 - Angiotensin converting enzyme (ACE) inhibitor
 - Angiotensin II receptor blocker
 - Aldosterone receptor blocker
 - Beta-blocker
 - Diuretics
 - Calcium channel blocker
 - Anti-Platelets
 - Anticoagulants
 - Antiarrhythmics
 - Cardiac glycosis (Digitalis)
 - Statins
 - Other vasodilators

- Other cardiac medication

5.5 Scheduled Follow-up

Scheduled follow-ups include 30-day, 1-, 2- and 3-year post procedure. Record the following information at each follow-up time point:

- Type of contact (visit)
- Date of contact
- TTE
- NYHA class
- Adverse event occurred or change in symptoms from previous follow-up
- Changes on cardiac medications (started/changed/stopped)
- Device Deficiency

5.6 TTE Follow-up

TTE is required at discharge and each annual follow-up visit.

5.7 Unscheduled Follow-up (only in case of reportable adverse event)

Complete Adverse Event form.

5.8 Device Deficiency during Follow-up Period

- Date device deficiency occurred
- Event occurred
- Adverse event (health hazard) relating to the device deficiency
- Background information/comment on the device deficiency
- Product information (Lot/Serial #)

5.9 Adverse Events (reportable events)

- Record the following adverse events in case report:
 - All heart failure and heart failure hospitalization adverse events
 - All other serious adverse events*
 - Events reported as relating to MitraClip or relationship to the device is unknown

- * A serious adverse event is defined as an event: lead to death; potentially leading to death; required in-patient hospitalization or prolongation of existing hospitalization for treatment; potentially leading to a persistent or significant disability or incapacity; led to a congenital disease or anomaly; or other event considered serious per physician's judgment.

Record whether each adverse event defined as above is related to MitraClip and/or the procedure, as well as outcome of the event. For serious adverse events, also record reason for the judgment as serious.

6. ENDPOINTS

6.1 Primary Endpoints

The primary endpoints of this study are single leaflet device attachment (SLDA) rate at 30 days and acute procedural success (APS) assessed at discharge. In the Surveillance, SLDA will be site reported. APS is defined as resulting MR reduction to $\leq 2+$ per echocardiographic assessment. If echocardiographic data at discharge was not available or unevaluable, echocardiographic data at 30 days will be used for evaluation. APS will not be achieved if a patient expired or received mitral valve surgery before discharge. Achievement of MR reduction to $\leq 2+$ as result of additional MitraClip implantation during index procedure will be considered as APS.

6.2 Other Endpoints

Other endpoints will be evaluated at the specific follow-up timepoints per typical mitral regurgitation intervention clinical studies, including but not limited to, mitral regurgitation severity score, NYHA class, LV function and anatomy, cardiac medication, adverse events, device deficiency. Rate of heart failure hospitalizations in the 1 year post-procedure will be compared to the 1 year prior to the index procedure.

7. Statistical Analysis

7.1 Analysis Populations

All patients registered in the surveillance with MitraClip treatment attempted will be included in the analysis.

7.2 Rationale for Sample Size Setting and the Assumptions

To establish an appropriate sample size for the Surveillance, SLDA, a low-occurrence event of (3%), was used as the event rate of interest. Table 1 presents SLDA rates through 1 year in the MitraClip clinical trials. SLDA was reported most frequently in the E-II RCT, the earliest clinical trial. SLDA

rates in the subsequent clinical trials consistently maintained at around 3% as investigators gained further experience with the MitraClip procedure.

Table 1: SLDA Rates through 1 Year in MitraClip Clinical Trials

	Successful MitraClip Implantation	SLDA	SLDA Rate
E-II RCT	158	10	6.3%
E-II HRR	75	1	1.3%
Realism HR (First 273 patients)	261	6*	2.3%
Realism HR (Subsequent 355 pts)	342	6	1.8%
AVJ-514 Clinical Trial	30	1**	3.3%

* One additional SLDA was reported after 1-year follow up (at 18-months follow-up), resulting in total number of the events of 7.

** SLDA was adjudicated by the core laboratory: not adjudicated by the site.

If the SLDA rate in the Surveillance is 3%, the upper limit of one-sided 95% confidence interval of the SLDA rate for a sample size of 250 patients would be 5.4%, which is lower than 6.3%, the SLDA rate in E-II RCT, the earliest MitraClip clinical trial. In other words, if the true SLDA rate is 3%, the SLDA rate in the Surveillance would be 5.4% or lower with a probability of approximately 95%.

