2.3 Endpoint Analysis

2.3.1 Primary Endpoint(s)

The primary analysis population is the Intent-to-treat (ITT) population. The primary endpoints of SLDA rate at 30 days and APS at discharge will be summarized with patient counts and percentages/rates, and exact 95% Clopper-Pearson confidence intervals as described in Section 2.2. Registered patients who do not have MitraClip procedure attempted will be excluded from the ITT population.

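### Does the sample-size rationale misread Table 1 by planning on a 3% SLDA rate and setting its 5.4% limit against 6.3%?

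*Protocol*

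**What the plan says.** Protocol 7.2 takes 3% as the SLDA rate of interest. It says the rate was highest in E-II RCT and that SLDA "rates in the subsequent clinical trials consistently maintained at around 3" per cent. The evidence is "Table 1: SLDA Rates through 1 Year in MitraClip Clinical Trials", whose denominators are successful implantations. A footnote on the single AVJ-514 event says that "SLDA was adjudicated by the core laboratory: not adjudicated by the site".

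The section then computes a one-sided 95% upper limit for 250 patients, which "would be 5.4%, which is lower than 6.3%, the SLDA rate in E-II RCT, the earliest MitraClip clinical trial".

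The endpoint is defined elsewhere. Protocol 6.1: "The primary endpoints of this study are single leaflet device attachment (SLDA) rate at 30 days", and "In the Surveillance, SLDA will be site reported". Protocol 7.1 sets the population: "All patients registered in the surveillance with MitraClip treatment attempted will be included in the analysis". SAP 2.3.1 sets the analysis: "The primary endpoints of SLDA rate at 30 days and APS at discharge will be summarized with patient counts and percentages/rates", with exact Clopper-Pearson intervals. Protocol 7.3 states that no hypothesis tests are pre-specified.

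**The concern.** The sentence about the later trials does not describe the table beneath it. Three of the four later rows are at 2.3% or lower, and the one row above 3% rests on a single event in 30 patients.

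The benchmark is also on a different scale from the endpoint. Table 1 counts SLDA through 1 year among implanted patients; the Surveillance will report SLDA at 30 days among all attempts. In the same patients a cumulative 30-day rate cannot exceed the 1-year rate, so setting a 30-day result against 6.3% can only flatter it. Section 7.2 does not draw this contrast, and neither document names a 1-year SLDA rate that would be like for like.

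If this mattered, the stated basis for the sample size of a primary safety endpoint would be unsound, or the result would be read too favourably against the first trial.

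**Working it through.** **1. The plan's own figure.** Inputs from Protocol 7.2: n = 250, rate 3%, one-sided 95%. The exact upper limit is the 0.95 quantile of Beta(x + 1, n − x). With x = 0.03 × 250 = 7.5 it is 5.45%, which agrees with the stated 5.4%. Whole-number counts bracket it: x = 7 gives 5.2% and x = 8 gives 5.7%. The figure stands.

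**2. What Table 1 shows.**

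| Cohort | SLDA / implanted | Rate | Exact 95% CI |
|---|---|---|---|
| E-II RCT | 10/158 | 6.3% | 3.1% to 11.3% |
| E-II HRR | 1/75 | 1.3% | 0.03% to 7.2% |
| Realism HR, first | 6/261 | 2.3% | 0.8% to 4.9% |
| Realism HR, subsequent | 6/342 | 1.8% | 0.6% to 3.8% |
| AVJ-514 | 1/30 | 3.3% | 0.1% to 17.2% |

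Later four rows: (1 + 6 + 6 + 1)/(75 + 261 + 342 + 30) = 14/708 = 1.98%, exact 95% CI 1.1% to 3.3%. All five rows: 24/866 = 2.8%. So 3% is not the observed later rate, but it lies inside the pooled interval and inside the interval of every later row.

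**3. Does 3% instead of 2% weaken the rationale?** Expected events in 250 are 7.5 at 3% and 250 × 14/708 = 4.9 at the pooled rate. With 5/250 = 2% observed, the upper limit is 4.2% instead of 5.4%. The limit falls below 6.3% when at most 9 events occur. That has probability 77.9% if the true rate is 3% and 97.2% if it is 1.98%. Planning on 3% therefore gives the less favourable picture on each measure.

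**4. The scale of the comparison.** The 5.4% is derived from 3%. The only support given for 3% is Table 1, and 6.3% is the first row of the same table. As a planning statement, both sides are through-1-year rates per implanted patient. The mismatch is between Table 1 and the endpoint.

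- *Window.* The direction is known. The size cannot be derived, because the documents give no 30-day counts. If the 30-day rate is below the 1-year rate, the limit at 250 patients will be tighter than 5.4%, so the precision statement errs on the safe side.
- *Denominator.* If the Realism HR cohort sizes of 273 and 355 are attempts (an assumption), the implanted shares are 261/273 = 95.6% and 342/355 = 96.3%. The rates move from 2.3% to 6/273 = 2.2% and from 1.8% to 6/355 = 1.7%. If E-II RCT had a similar share (also an assumption), 6.3% becomes 6.33% × 0.956 = 6.1%, still above 5.4%. The direction is not certain, because the table does not define successful implantation.

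**5. Where 6.3% is used.** Only in Protocol 7.2. It does not appear in the SAP, and SAP 2.3.1 reports counts, percentages and exact intervals with no comparator.

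**The case for a change.** The best case for acting is that this paragraph is the only stated rationale for the sample size, it concerns a primary safety endpoint, and the results go to a regulator. A reader may well repeat the 6.3% comparison with the observed 30-day rate. Two corrected sentences and one supporting row for 1-year SLDA in implanted patients would prevent that at little cost.

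Part of this stands. The sentence about the later trials is loose, and section 7.2 does not contrast the table's window and denominator with those of the endpoint.

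The rest is weaker. Section 7.2 gives the 1-year window in its text and in the table title, and the column heading gives the denominator, so a reader who makes the comparison has what is needed to qualify it. The feared misreading depends on a comparison that neither document plans.

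The extra row is also less simple than it sounds. Its denominator could not be matched to Table 1 with confidence, and a plain percentage at 1 year would need rules for death and dropout. Protocol 2.2 also waives follow-up after a failed attempt treated by other means, unless a related adverse event occurs. Adverse events and device deficiencies are recorded at every scheduled visit (Protocol 5.5), and SAP 2.2.3 provides Kaplan-Meier methods, so a 1-year SLDA rate can be produced if someone wants it.

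Dropping the AVJ-514 event because the core laboratory adjudicated it (13/708 = 1.8%) adds nothing firm. The documents do not say how SLDA was adjudicated in the other trials, so the remaining events are not known to be site reported.

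**Conclusion.** No change follows. The description of the later trials is imprecise: the observed rate is 2.0% (range 1.3% to 3.3%), and 3% is best read as a conservative planning value. That costs nothing. The 5.4% limit reproduces, it would be 4.2% at a 2% rate, and both are below 6.3%.

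The 6.3% is a rough reference in any case, with an exact interval of 3.1% to 11.3%, and it serves only to give scale to the precision statement. Rewording the section would alter no sample size, estimate, interval or decision.

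This rests on two things: the Surveillance stays descriptive, as Protocol 7.3 says, and anyone who sets the final 30-day rate beside Table 1 notes the table's stated window and denominator. The size of the window effect is unknown from these documents, but its direction makes the planning cautious.

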7.3 Statistical Analyses

No pre-specified hypothesis tests are planned for this surveillance. Descriptive analysis will be performed to summarize baseline, procedural, clinical and safety event data. Depending on the type of data (e.g., continuous or categorical), statistical methods described in this section below will be used.

For continuous variables such as age, results will be summarized with the numbers of observations, means, standard deviations, and 95% confidence intervals for the mean. These calculations will be done under the assumption that the data are approximately normal in distribution.

For time to event data such as all-cause mortality, Kaplan-Meier analyses will be used.

For recurrent event data such as recurrent heart failure hospitalizations post-procedure, data will be analyzed using a generalized linear model, such as Poisson regression model.

8. ANALYSIS AND REPORTING

1.0 SYNOPSIS OF STUDY DESIGN

1.1 Purpose of the Statistical Analysis Plan

This statistical analysis plan (SAP) is to provide a detailed and comprehensive description of the planned methodology and analysis to be used for the AVJ 17-519 MitraClip NT System Post-marketing Surveillance (PMS) clinical investigation. This SAP is based on the Version 1.0, Jan 04, 2018 Clinical Investigation Plan (CIP).

1.2 Clinical Investigation Objectives

The purpose of this post-marketing clinical use surveillance (hereinafter referred to as “Surveillance”) is to observe the frequency, type and degree of adverse device effects and adverse events in order to assure the safety of the new medical device, and to collect safety and efficacy information for evaluating the results of the clinical use.

1.3 Clinical Investigation Design

AVJ 17-519 is a prospective, multi-center, single-arm surveillance study of patients with moderate to severe and severe mitral regurgitation (3+ and 4+ MR) in whom a MitraClip implant was attempted (Marketing Approval No. 22900BZX00358000, October 31, 2017, hereinafter referred to as “MitraClip”). Information will be collected for up to 3 years post procedure.

- Approximate preparation period: 6 months
- Registration period: Approximately 2 years
- Follow-up period: 3 years
- Final re-examination report: 6 months
- Total PMS period: Approximately 6 years

1.4 Endpoints

1.4.1 Primary Endpoint(s)

The primary endpoints of this study are: a) the rate of single leaflet device attachment (SLDA) at 30 days; and b) acute procedural success (APS) assessed at discharge. The SLDA rate will be calculated based on site reported observations. APS is defined as successful implantation of the MitraClip device with resulting MR reduction to $\leq 2+$ per echocardiographic assessment. If echocardiographic data at discharge is not available or unevaluable, echocardiographic data at 30 days will be used for evaluation. APS will not be achieved if a patient expired or received mitral valve surgery before discharge. Achievement of MR reduction to $\leq 2+$ as result of additional MitraClip implantation during index procedure will be considered as an APS.

